5 STUDY DESIGN

5.1 Overall Design

Study CA2096GE is a multicenter, open-label, Phase 3 study. **Per Protocol Amendment 01, PK co-primary endpoints, secondary endpoints, [REDACTED] of the study have been removed. Efficacy, PROs, and biomarker analyses will not be completed. Samples already collected for PK and immunogenicity assessments will be analyzed bioanalytically for nivolumab concentrations and ADAs and reported as listings. Further collections for PK, ADAs, biomarkers, and PROs will be discontinued. Only safety assessments will be conducted.** Therefore, the study design has been adapted to reflect the Protocol Amendment 01 changes, [REDACTED]. Part 1 is no longer hypothesis-driven, but rather descriptive in nature (Arm A and Arm B), with the primary objective being safety and tolerability and exploratory objective as described in [Table 4-1](#).

- Arm A (n = 6):

- [REDACTED]

[figure not shown]
- Arm B (n = 8):

- Nivo IV (BMS-936558) 240 mg Q2W for Cycles 1 through 4.
 - Nivo IV 480 mg Q4W Cycle 5 onwards for up to total of 52 weeks.
 - All dosing will be performed in-clinic.

Participants will be stratified by stage (Stage IIIA/B vs Stage IIIC/D/IV) per AJCC 8th edition [REDACTED]

All participants will be treated until recurrence of disease, unacceptable toxicity, participant withdrawal of consent, death, or a maximum of 52 weeks of treatment from first dose, whichever occurs first.

The study design schema is presented in [Figure 5.1-1](#).

Figure 5.1-1: Study Design Schema

Abbreviations: AJCC, American Joint Committee on Cancer; CNS, central nervous system; FU, follow-up; IV, intravenous; N, number of participants; Nivo, nivolumab; PK, pharmacokinetic, Q2W, every 2 weeks; Q4W, every 4 weeks; RT, radiation therapy; SC, subcutaneous; vs, versus.

^a Treatment until recurrence of disease, unacceptable toxicity, participant withdrawal of consent, death, or a maximum of 52 weeks of treatment from first dose, whichever occurs first.

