Results of efficacy surveillance must be reviewed by investigator and documented before dose administration of the next cycle.

Participant safety will be preserved through:

- Protocol-defined visits to the clinic
- Phone communication with the participant (see [Section 9.4.5](#))
- Regular monitoring of labs and symptoms
- Other safety reporting to the HCP by the participant or the participant's caregiver
- All participants will be treated until recurrence of disease, unacceptable toxicity, participant withdrawal of consent, death, or a maximum of 52 weeks of treatment from first dose, whichever occurs first.

[figure not shown]
Biomarker assessments are no longer applicable per Protocol Amendment 01.

[figure not shown]
5.1.2.1 *Randomized Study Cohort*

Arm A: Participants randomized to Arm A will receive [REDACTED] with rHuPH20 [REDACTED]
[REDACTED]
[REDACTED]

Arm B: Participants randomized to Arm B will receive Nivo IV 240 mg Q2W during the first 4 cycles. Following Cycle 4, participants will receive Nivo IV 480 mg Q4W. All doses/visits will be in-clinic.

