Nivolumab monotherapy was originally approved as a body weight-based dose of 3 mg/kg IV Q2W and was recently updated to flat-dosing regimens of 240 mg Q2W or 480 mg Q4W in multiple indications. For this study, the selected dose of 240 mg via IV Q2W is per dose/schedule approved for this patient population. In addition, there is extensive PK, safety, and efficacy data available at this dose across multiple tumors and dosing regimens. Global development with flat doses of nivolumab are ongoing in a broad range of clinical trials in a variety of additional tumor types. Based on the aforementioned nivolumab 240 mg IV Q2W is considered an appropriate and globally accepted comparator to [REDACTED]

In relation to transition to 480 mg IV Q4W, most recently, data from the comparator arm in study CA209915 support that the activity of flat dose (480 mg IV Q4W) nivolumab performs similarly to the originally assessed 3 mg/kg IV Q2W dosing schedule in study CA209238.

Additional details on nivolumab posologies and risk-benefit can be found in the BMS-936558 investigator brochure.

[REDACTED]

5.5.4 *Rationale for Switch from Q2W to Q4W (Arm B [IV])*

In order to mitigate participant burden, a switch from Q2W to Q4W will occur after Cycle 5 for participants in Arm B receiving IV nivolumab. Cycle 5 has been selected as the time for the switch as it was the time at which the primary endpoints in the original study design were being collected.

5.5.5 *Rationale for Continued Adjuvant Therapy for Participants Who Are Diagnosed with Melanoma in Situ During Study Treatment*

Malignant melanoma in situ (MMIS) Stage 0 includes Tis, N0, M0, demonstrates a radial growth phase in which the proliferation of malignant melanocytes is confined to the epidermis. Patients with a new Stage 0 melanoma are at minimal risk from that new tumor. The risk of death develops from advanced Stage IIIB/C/D or Stage IV melanoma for which they are receiving treatment during the clinical trial. Opdivo (nivolumab) is approved for the adjuvant treatment of adult patients with melanoma with involvement of lymph nodes or metastatic disease who have undergone complete resection. Consequently, in the absence of intolerable toxicity, patients with diagnosed MMIS should continue adjuvant therapy using the same dose and schedule for their original melanoma for a maximum of 1-year total duration starting from first dose (maximum of 13 doses). Melanoma in situ will not be considered a new primary malignancy.

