7.1 Study Interventions Administered

Table 7.1-1: Study Interventions

ARM Name	Arm A Nivolumab SC [REDACTED]	Arm B Nivolumab IV
Intervention Name	Nivolumab/rHuPH20 BMS-986298	Nivolumab BMS-936558
Type	[REDACTED]	Drug
Dose Formulation	SC injection	Solution for injection ^a
Dosage Level(s)	Nivolumab 600 mg [REDACTED] Once Q2W for up to 52 weeks	Nivolumab 240 mg Q2W for 16 weeks (8 doses) Nivolumab 480 mg Q4W for 36 weeks (9 doses)
Route of Administration	SC injection	IV infusion
IMP and Non-IMP	IMP	IMP
Sourcing	Provided centrally by the Sponsor	Provided centrally by the Sponsor
Packaging and Labeling	[REDACTED]	Study intervention will be provided in vial(s) in a carton. Each vial(s) and carton will be labeled as required per country requirement.
Current/Former Name(s) or Alias(es)	N/A - see intervention name	Opdivo

Abbreviations: [REDACTED]; IMP, investigational medicinal product; IV, intravenous; N/A; not applicable; [REDACTED] Q2W, every 2 weeks; Q4W, every 4 weeks; rHuPH20, recombinant human hyaluronidase PH20 enzyme; SC, subcutaneous; U, units.

^a “Concentrate for Solution for Infusion” is also being used for certain countries for dose formulation to align with the commercial Opdivo product.

7.1.1 *Study Treatment Details for Intravenous Administration of Nivolumab*

Participants randomized to Arm B will receive nivolumab at a dose of 240 mg over an approximately 30-minute IV infusion Q2W on Days 1 and 15 of the first 4 treatment cycles. Subsequently, participants will receive nivolumab at a dose of 480 mg over an approximately 30-minute IV infusion Q4W on Day 1 of each treatment cycle starting at Cycle 5, Day 1 until disease recurrence, unacceptable toxicity, withdrawal of consent, a maximum of 52 weeks of treatment from first dose, death, or the end of study, whichever occurs first. If needed, flush the intravenous line with an appropriate amount of diluent (eg, 0.9% Sodium Chloride or 5% Dextrose in water) to ensure that the complete dose is administered over approximately 30 minutes. Begin study treatment within 3 calendar days of randomization.

[figure not shown]
There will be no intra-participant dose escalations or reductions of nivolumab allowed. For Q2W dosing cycles, participants may be dosed no less than 12 days from the previous dose. The dosing window is \pm 3 days. Premedications are not recommended for the first dose of nivolumab.

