8 DISCONTINUATION CRITERIA

8.1 Discontinuation From Study Intervention

Participants MUST discontinue IP (and Non-IP/AxMP at the discretion of the investigator) for any of the following reasons:

- Participant's request to stop study intervention. Participants who request to discontinue study intervention will remain in the study and must continue to be followed for protocol-specified follow-up procedures. The only exception to this is when a participant specifically withdraws consent for any further contact with him/her or persons previously authorized by the participant to provide this information
- Any clinical AE, laboratory abnormality, or intercurrent illness which, in the opinion of the investigator, indicates that continued participation in the study is not in the best interest of the participant
- Termination of the study by BMS
- Loss of ability to freely provide consent through imprisonment or involuntarily incarceration for treatment of either a psychiatric or physical (eg, infectious disease) illness. (Note: Under specific circumstances and only in countries where local regulations permit, a participant who has been imprisoned may be permitted to continue as a participant. Strict conditions apply, and BMS approval is required.)
- Disease recurrence (local, regional, or distant)
- Additional protocol-specified reasons for discontinuation ([Section 8.1.1](#))
- Pregnancy (refer to [Section 9.2.5](#))
- Significant noncompliance with protocol (eg, procedures, assessments, medications, etc.). The investigator should discuss such issues with the Medical Monitor.

Refer to the Schedule of Activities for data to be collected at the time of treatment discontinuation and follow-up and for any further evaluations that can be completed.

All participants who discontinue study intervention should comply with protocol-specified follow-up procedures as outlined in [Section 2](#). The only exception to this requirement is when a participant withdraws consent for all study procedures, including post-treatment study follow-up, or loses the ability to consent freely (eg, is imprisoned or involuntarily incarcerated for the treatment of either a psychiatric or physical illness).

If study intervention is discontinued prior to the participant's completion of the study, the reason for the discontinuation must be documented in the participant's medical records per local regulatory requirements in each region/country and entered on the appropriate CRF page.

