9.1.3.3 Definitions

Recurrence is defined as the appearance of one or more new melanoma lesions (except MMIS), which can be local, regional, or distant in location from the primary resected site.

Local Cutaneous Recurrence

Local recurrence is defined as tumor regrowth within 2 cm of the surgical incision following definitive excision of a primary melanoma with appropriate surgical margins. Lesions must be unequivocal. Local cutaneous recurrence after adequate excision of the primary melanoma is associated with aggressive tumor biologic features and is frequently a harbinger of metastases.

In Transit Metastasis Recurrence

Any skin or subcutaneous metastases more than 2 cm from the primary melanoma lesion, but not beyond the regional lymph node. When present, in transit metastases are usually multiple, evolve over time, and, as previously stated, are often the harbinger of subsequent systemic disease.

Regional Nodal Recurrences

Regional node failure, usually at the periphery of the prior surgical procedure. Lesions must be unequivocal as noted in [Table 9.1.3.2-1](#).

Distant Recurrence

Any distant metastases with radiographic appearance consistent with tumor recurrence or positive histology/cytology (typically defined as any M except for M0). Distant metastases include node relapses beyond the anatomical compartment of the primary melanoma basin, a nodal basin situated in a different anatomical compartment beyond the primary melanoma lesion, or in 2 nodal basins (even if contiguous; ie, 2 pelvic nodal basins, 2 mediastinal nodal basins, etc).

Considerations for establishing distant recurrence on cross-sectional imaging:

- CT and MRI are an important part of the work-up to establish recurrence. Contrast-enhanced CT and MRI are the preferred imaging modalities. See [Section 9.1.1](#) for details.
- Positron emission tomography (PET) alone will not be considered for the disease assessment. Complementary CT and/or MRI or biopsy must be performed in such cases.
- Cytology and/or histology are mandatory to confirm recurrence in solitary or in doubtful lesions, cutaneous, subcutaneous, or lymph node lesions. Histological or cytological evidence

of recurrence should be attempted in all cases (except for brain metastases) when safe and clinically feasible.

Clinically detected new lesions:

- The neoplastic nature of superficial cutaneous lesions must be confirmed by cytology/histology.

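### Section 5.5.5 caps treatment after a melanoma in situ diagnosis at 13 doses from first dose, but one year is 26 doses in Arm A and 17 in Arm B

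*Combined protocol and SAP*

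**What the plan says.** Section 5.5.5 says that a participant diagnosed with melanoma in situ during treatment should, absent intolerable toxicity, continue adjuvant therapy on the same dose and schedule "for a maximum of 1-year total duration starting from first dose (maximum of 13 doses". Both limits count from the first dose, not from the diagnosis.

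The other sections on duration give a limit in weeks and no cap on the number of doses:

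- Section 5.1: "or a maximum of 52 weeks of treatment from first dose, whichever occurs first".
- Section 5.1.2: "All participants will be treated until recurrence of disease, unacceptable toxicity, participant withdrawal of consent, death, or a maximum of 52 weeks".
- Section 7.1.1 (Arm B): "a maximum of 52 weeks of treatment from first dose, death, or the end of study, whichever occurs first".

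Table 7.1-1 sets the schedules. Arm A receives 600 mg "Once Q2W for up to 52 weeks". Arm B receives "Nivolumab 240 mg Q2W for 16 weeks (8 doses) Nivolumab 480 mg Q4W for 36 weeks (9 doses".

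Section 9.1.3.3 keeps melanoma in situ out of recurrence: "Recurrence is defined as the appearance of one or more new melanoma lesions (except MMIS". The entry in the Section 8.1 discontinuation list that might otherwise apply is "Disease recurrence (local, regional, or distant", so a diagnosis of melanoma in situ does not trigger it.

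**The concern.** The sentence in Section 5.5.5 asks for three things: the participant's existing schedule, treatment for up to a year, and no more than 13 doses. In both arms the dose limit is reached well before the year ends, so a participant who keeps the schedule cannot complete the year. No reason is given for a shorter course. The paragraph argues the opposite, that the new in situ lesion carries little risk and treatment of the original melanoma should go on.

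Although it sits under the dose rationale, the sentence is worded as an instruction. It is also the protocol's only explicit direction on dosing after melanoma in situ, so a site with such a case would look there. A site that followed the number would stop adjuvant therapy before the 52 weeks allowed elsewhere.

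**Working it through.** **Inputs.** Maximum duration 52 weeks from first dose (Sections 5.1, 5.1.2, 7.1.1). Arm A: 600 mg every 2 weeks. Arm B: 240 mg every 2 weeks for 16 weeks, then 480 mg every 4 weeks for 36 weeks (Table 7.1-1). Cycle length 28 days (Tables 2-2 and 2-3). Enrollment paused 26-Oct-2022 (Section 5.1.4). First dose within 3 calendar days of randomization (Table 2-1). Amendment 01 issued 25-May-2023.

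**Where 13 comes from.** Dosing every 4 weeks throughout gives 52/4 = 13 doses. Neither arm uses that regimen. Thirteen is also the number of 28-day cycles in 52 weeks, and Section 7.4.3 runs to Cycle 13.

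**Doses in one year under the actual schedules.**

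- Arm A: 52/2 = 26. Table 2-2 agrees: two doses in each of Cycles 1–4, two in Cycle 5 and two in each of Cycles 6–13, so 8 + 2 + 16 = 26.
- Arm B: 8 + 9 = 17, as printed in Table 7.1-1.

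**What a 13-dose cap does, with no delays.**

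| | Arm A | Arm B |
|---|---|---|
| Week of 13th dose | 12 × 2 = 24 | 16 + 4 × 4 = 32 |
| Doses not given | 26 − 13 = 13 | 17 − 13 = 4 |
| Full-year total | 26 × 600 = 15,600 mg | 8 × 240 + 9 × 480 = 6,240 mg |
| Total under the cap | 13 × 600 = 7,800 mg | 8 × 240 + 5 × 480 = 4,320 mg |

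**What could still be lost at the amendment date.** The section did not exist before 25-May-2023, so only later doses are at risk. The latest possible first dose is 26-Oct-2022 + 3 days = 29-Oct-2022, which is 208 days before 25-May-2023.

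- Arm A: doses given = floor(208/14) + 1 = 15. Remaining 26 − 15 = 11, all beyond 13. Loss 11 × 600 = 6,600 of 15,600 mg, or 42%.
- Arm B: doses given = 8 + floor((208 − 112)/28) + 1 = 12. Remaining 17 − 12 = 5, of which the first is the 13th dose and 4 are beyond it. Loss 4 × 480 = 1,920 of 6,240 mg, or 31%.

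**Dependence on the first-dose date.**

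- Arm A: the loss of 11 needs a first dose on 28 or 29-Oct-2022. It falls by one dose for each 14 days of earlier start. It is zero for a first dose by 09-Jun-2022, because the 26th dose is due on day 350.
- Arm B: the loss is 4 for a first dose from 16-Sep to 29-Oct-2022. It falls by one dose for each 28 days of earlier start. It is zero for a first dose by 23-Jun-2022, because the 17th dose is due on day 336.

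**The case against.** The best reply is that this is a slip, not a second stopping rule. The same sentence states the one-year limit and the unchanged schedule, the parenthesis is a mistaken gloss on that year, and the dosing sections consistently say 52 weeks. Two ceilings are not logically incompatible. An undelayed Arm A participant still on treatment had already received at least 15 doses when the amendment was issued, so the figure is visibly wrong and a site is as likely to query it as to stop.

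Much of this stands, and it is why the point is minor. A slip is the likely origin, and the two maxima can formally coexist. But the text says doses, not cycles, and reading it as a slip concedes that the number is wrong. In Arm B the error shows less easily, because an undelayed participant could have received as few as 12 doses by that date.

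Two narrower points also stand. The silence of Section 8.1 on a dose count is weak support, because that list does not name the 52-week maximum either. And sites can apply an amendment only after ethics approval (Appendix 2), so their operative date is later than 25-May-2023. That is a second reason to treat the losses as upper bounds.

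**Conclusion.** The concern holds, at minor severity. The 13-dose figure is wrong for both arms: one year is 26 doses in Arm A and 17 in Arm B. Read literally, it would stop treatment before the 52-week limit that already applies to these participants.

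For an undelayed participant still on treatment at the amendment date, the loss ranges from 0 to 11 doses in Arm A and from 0 to 4 in Arm B. The upper ends assume the latest possible first dose and that the amendment takes effect on its issue date. First-dose dates and the number still on treatment are not stated. Any loss also needs an on-study melanoma in situ diagnosis, and none is reported among the 14 participants (6 in Arm A, 8 in Arm B). The primary safety tabulations and listings are not affected.

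**What to change.** Delete the parenthesis with the dose count from Section 5.5.5, so that the limit of one year from first dose stands alone. If a count is wanted, state a maximum of 26 doses in Arm A and 17 in Arm B.

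Deletion is cleaner. Section 5.5.4 places the Arm B switch after Cycle 5, which read literally would give 10 + 8 = 18 doses. Table 7.1-1 and Section 7.1.1 start dosing every 4 weeks at Cycle 5, Day 1 and support 17.

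The cost is one wording correction, which an administrative letter could carry. The visit schedule, data collection and analysis do not change.

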5.6 Clinical Pharmacology Summary

5.6.1 Clinical Pharmacology of Nivolumab

Nivolumab pharmacokinetics (PK) was assessed using a population PK approach for single-agent nivolumab.

Nivolumab as a single agent: The PK of single-agent nivolumab was studied in patients over a dose range of 0.1 to 20 mg/kg administered as a single dose or as multiple doses of nivolumab as a 60-minute intravenous infusion every 2 or 3 weeks. Nivolumab clearance (CL) decreases over time, with a mean maximal reduction (% coefficient of variation [CV%]) from baseline values of 24.5% (47.6%) resulting in a geometric mean steady-state clearance (CLss) (CV%) of 8.2 mL/h (53.9%) in patients with metastatic tumors; the decrease in CLss is not considered clinically relevant. Nivolumab clearance does not decrease over time in patients with completely resected melanoma, as the geometric mean population clearance is 24% lower in this patient population compared with patients with metastatic melanoma at steady-state. The geometric mean volume of distribution at steady-state (Vss) (CV%) is 6.8 L (27.3%), and geometric mean elimination half-life (t_{1/2}) is 25 days (77.5%). Steady-state concentrations of nivolumab were reached by 12 weeks when administered at 3 mg/kg every 2 weeks, and systemic accumulation was 3.7-fold. The exposure to nivolumab increases dose proportionally over the dose range of 0.1 to 10 mg/kg administered every 2 weeks. The predicted exposure (C_{avg} and C_{max}) of nivolumab after a 30-minute infusion is comparable to that observed with a 60-minute infusion.

Specific Populations: The population PK analysis suggested that the following factors had no clinically important effect on the clearance of nivolumab: age (29 to 87 years), weight (35 to 160 kg), gender, race, baseline LDH, PD-L1 expression, solid tumor type, tumor size, renal impairment, and mild hepatic impairment.

Renal Impairment: The effect of renal impairment on the clearance of nivolumab was evaluated by a population PK analysis in patients with mild (eGFR 60 to 89 mL/min/1.73 m²), moderate (eGFR 30 to 59 mL/min/1.73 m²), or severe (eGFR 15 to 29 mL/min/1.73 m²) renal impairment. No clinically important differences in the clearance of nivolumab were found between patients with renal impairment and patients with normal renal function.

Hepatic Impairment: The effect of hepatic impairment on the clearance of nivolumab was evaluated by population PK analyses in patients with HCC and in patients with other tumors with

mild hepatic impairment (total bilirubin [TB] less than or equal to the ULN and AST greater than ULN or TB greater than 1 to $1.5 \times$ ULN and any AST) and in HCC patients with moderate hepatic impairment (TB greater than 1.5 to $3 \times$ ULN and any AST). No clinically important differences in the clearance of nivolumab were found between patients with mild/moderate hepatic impairment.

Full details on the clinical pharmacology aspects of nivolumab can be found in the Investigator Brochure and product label.

Full details regarding approved nivolumab dosages in their associated indications may be found in the product label.

5.6.2 Clinical Pharmacology of Recombinant Human Hyaluronidase PH20

rHuPH20 may enable coadministered therapeutics to overcome administration time and volume barriers to SC drug delivery. Overall, data from a number of studies suggest that rHuPH20 can increase the utility of SC drug administration by improving ease of administration and the PK profile of concurrently administered large proteins. The half-life of rHuPH20 in skin is < 30 minutes, and the local permeability barrier in these tissues is restored to pre-injection levels within 24 hours to 48 hours after injection of hyaluronidase.^{35,36} A study showed that rHuPH20 was not detectable systemically in healthy volunteers and patients following SC administration at doses of 10,000 U and 30,000 U with a currently marketed monoclonal antibody product.³⁷ Another study of the PK of rHuPH20 (Halozyme Study HALO-104-104) demonstrated that plasma concentrations of rHuPH20 rapidly declined, with a very short $t_{1/2}$ (≤ 10.4 minutes) and the plasma concentration became undetectable (< 0.03 ng/mL) within 1.5 hours after the end of the IV infusion for IV doses of 10,000 or 30,000 units of rHuPH20.³⁸

As of Dec-2022, 1,592 participants were exposed to HYLENEX and other rHuPH20 DPs in 30 clinical studies conducted under Investigational New Drug 66,888 or in postmarketing Phase 4 studies. In these studies, the maximum duration of exposure was 12 weeks, and individual doses ranged from 15 U to 96,000 U rHuPH20. In partnered trials with co-administered therapeutics, more than 9,000 participants were exposed.²⁰

In partnered trials, the maximum duration of participant exposure to rHuPH20 was up to 3.5 years (187.69 patient-years) in the combined pivotal and safety extension studies for HYQVIA® (Immune Globulin Infusion 10% [Human] With Recombinant Human Hyaluronidase). One Halozyme study evaluated rHuPH20 injected intradermally as a single agent, 28 studies evaluated rHuPH20 injected SC immediately prior to another agent or coadministered SC with another agent, and 13 studies evaluated rHuPH20 coformulated with recombinant human insulin (insulin-PH20) or rapid-acting insulin analogs (aspart-PH20 and lispro-PH20). One Halozyme IV dosing study was conducted using 10,000 U or 30,000 U of rHuPH20 in healthy volunteer participants. All but 2 Halozyme studies were conducted in adult populations; pediatric exposure (< 18 years of age) in 2 clinical studies included 139 participants with mild-to-moderate dehydration who received SC infusions of isotonic fluids.

Across all studies, SC injections of rHuPH20 were generally well tolerated in healthy participants, dehydrated pediatric participants, hospice and palliative care participants, participants with type 1

and 2 diabetes, and participants with rheumatoid arthritis. SC injections of rHuPH20 either alone or co-administered with lactated Ringer's, normal saline, co-injected drugs (morphine, ceftriaxone, insulin, and insulin analogues), or biologic products (immunoglobulin G and adalimumab) have been well tolerated in all clinical trials. Most AEs were mild, transient injection-site reactions, including erythema, pain, bruising, pruritus, burning, tenderness, edema, induration, irritation, paresthesia, numbness, and rash. Moderate injection-site reactions, which have occurred less frequently, included burning, erythema, pain, and numbness. Mild-to-moderate headache was also commonly reported. AEs in these trials have otherwise generally reflected the adverse reaction profiles of the co-administered drug or have been associated with the rapid introduction of a relatively large volume of fluid into the SC space.

Antibodies to rHuPH20 have been evaluated in several nonclinical and clinical studies. To date, no clinical signs or symptoms have been associated with positive binding or neutralizing antibodies titers in clinical trials with rHuPH20 and no confirmed rHuPH20-neutralizing antibody activity has been detected. In addition to these studies, a large clinical safety database exists for rHuPH20 as a tissue permeability enhancer co-administered with several approved products in the US and/or Europe (European Union), including:

- DARZALEX FASPRO™ (daratumumab and hyaluronidase-fihj);
- PHESGO™ (pertuzumab, trastuzumab, and hyaluronidase-zzxf; US only);
- HYQVIA® (Immune Globulin Infusion 10% [Human] with rHuPH20);
- Herceptin® SC/HERCEPTIN HYLECTATM (trastuzumab coformulated with rHuPH20);
- MabThera® SC/RITUXAN HYCELIA® (rituximab coformulated with rHuPH20); and
- HYLENEX® (rHuPH20 alone; US only).

